#### 7.2.3. Pharmacokinetic Analysis

Plasma concentrations of ManNAc and free Neu5Ac will be summarized descriptively by collection time points, and figures will be provided to plot the mean concentrations over time by dose along with individual subject results. Reporting will be carried out according to ICH guidelines (ICH-E3).

The following PK parameters may be estimated using noncompartmental analyses to assess the concentration-time data:  $C_{max}$ ,  $T_{max}$ ,  $AUC_{last}$ ,  $AUC_t$ ,  $AUC_{0-\infty}$ ,  $t_{1/2}$  and  $C_{trough}$  plasma concentrations.

In addition, the  $C_{max}$  geometric mean and corresponding 95% confidence interval may also be provided.

Day 1 and Day 8 data for  $C_{\max}$  and  $AUC_t$  may be compared to determine the accumulation ratio of the compound.

#### **7.2.4. Pharmacodynamics**

Different dose levels will be evaluated by a statistical dose-response model of the relationship between dose and the rate at which plasma free Neu5Ac returns to baseline levels.

The following PD parameters may be summarized and analyzed by treatment group: Intracellular ManNAc, Neu5Ac, CMP-Neu5Ac and plasma sialylation (may include T/ST ratios). A similar statistical dose-response model may be used to evaluate these parameters, if appropriate.

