**APPENDIX D. BLOOD/URINE SAMPLING SCHEDULE****Baseline and Pharmacokinetic Phase**

Sample	Timepoints																						Sample	Blood Volume (mL)	Lab		
	Baseline	PK Phase																				Safety Phase					
		Day 1 (hours post-dose)										Day 2-6	Day 7 (hours after last dose)													Day 8-10	
		Pre 	0.5	1	2	3	4	6	8	10	12 	Pre 	Pre 	0.5	1	2	3	4	6	8	10	12					
Blood PK 	X	X	X	X	X	X	X	X	X	X	X	X	X	X	X	X	X	X	X	X	X	X		Blood	3	Alliance	
Clinical labs 	X											X	X											X	Blood/ Urine	14.5	NIH DLM
PD 	X							X		X	X	X	X											X	Blood	20	Alliance
Research labs 	X											X	X											X	Blood/ Urine	10-30	[name]/ TRND
Urine PK 		X		X		X		X			X	X	X														

Blood for plasma PK analysis will be collected on Day 1 at pre-dose and at 0.5, 1, 2, 3, 4, 6, 8, 10, 12 hours after the first administration of study drug. Note that 12-hour timepoint should be collected immediately before administering the evening dose of study drug (trough level).

On Days 2-6 (weekdays only), samples will be collected immediately before administering the morning dose of the study drug.

On Day 7, blood will be collected before the morning dose and at 0.5, 1, 2, 3, 4, 6, 8, 10 and 12 hours after morning administration of study drug. Note that 12-hour timepoint should be collected immediately before administering the evening dose of study drug (trough level) (Section 5.2.3)

Collection of trough blood samples (immediately before drug administration).

Clinical laboratory test will be collected to perform safety evaluation at baseline, on Day 2, 5 and 8 ( $\pm 1$ ). Subjects in Cohort A will have an additional test on Day 10 ( $\pm 1$ ). Clinical laboratory tests will include CBC with differential, platelet count, reticulocyte count, ESR, C-reactive protein, PT, and PTT, acute care panel (sodium, potassium, chloride, carbon dioxide, glucose, creatinine, blood urea nitrogen (BUN)), mineral panel (albumin, calcium, magnesium, phosphorus), hepatic panel (alkaline phosphatase, alanine aminotransferase (ALT), aspartate aminotransferase (AST), direct bilirubin), GGT, lipid panel, creatine kinase, and cystatin-C, urinalysis, and pregnancy test (Section 5.2.2)

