**Safety/Efficacy Phase and Final Pharmacokinetic Phase**

Sample	Timepoints																	Sample	Blood Volume (mL)	Lab				
	Safety/Efficacy Phase		Terminal PK													Safety/Efficacy Phase								
	Day 45 (±5 days)	Day 85 (±5 days)	Day 90 (-5 days)													Day 180 (±5 days)	Day 365 (±5 days)				Day 450 (±30 days)	Day 548, 730 (±30 days)	Day 638, 820 (±30 days)	Day 912 (±30 days)
			Pre 	0.5	1	2	3	4	6	8	10	12	24	48	72									
Blood PK 	X	X	X	X	X	X	X	X	X	X	X	X	X	X	X	X	X	X	X	X	Blood	3	Alliance	
Clinical labs 	X	X													X		X	X	X	X	X	Blood/ Urine	14.5	Various
Research labs 	X	X													X		X		X			Blood/ Urine	10-30	[name]
PD 	X	X	X												X		X		X			Blood	20	Various

Blood for plasma PK analysis will be collected on Day 45, 85, 180, 365, 548 and 730 (±5 days) immediately before administering the morning dose of the study drug (though levels). On Day 90 (-5 days), blood will be collected for terminal PK at pre-dose and at 0.5, 1, 2, 3, 4, 6, 8, 10, 12, 24, 48 and 72 hours after administration of study drug. Drug will be withheld for 72 hours (Section 5.2.3). On Day 912, PK will be collected at 2, 4, 6, 8, 24 and 48 hours after the first study drug administration on TID dosing. Plasma will be collected right before ManNAc dose (trough) at the 8, 24 and 48 hour timepoints. Patient will avoid ingestion of ManNAc for 5-7 days prior to pre-dose PK draw on TID dosing.

Collection of trough blood samples (immediately before drug administration)

Clinical laboratory evaluations will be collected at baseline and on Days 45, 85, 90, 180, 365, 548, 730, 820, 912 (±5 days), and 24-48 hours after last administration of study drug and will include CBC with differential, platelet count, reticulocyte count, ESR, C-reactive protein, PT, and PTT, acute care panel (sodium, potassium, chloride, carbon dioxide, glucose, creatinine, blood urea nitrogen (BUN), mineral panel (albumin, calcium, magnesium, phosphorus), hepatic panel (alkaline phosphatase, alanine aminotransferase (ALT), aspartate aminotransferase (AST), direct bilirubin), lipid panel, creatine kinase, and cystatin-C, urinalysis, and pregnancy test (Section 5.2.2). Day 450 and 638 will include all clinical labs except pregnancy test and lipid profile.

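### Section 7.2.4 models dose against the rate of Neu5Ac return to baseline, but the return is sampled off drug at only one planned dose; the optional accumulation ratio in 7.2.3 names a day with no PK sample

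*Combined protocol and SAP*

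**What the plan says.** Section 7.2.4 states, without qualification, that dose levels will be evaluated by a "dose-response model of the relationship between dose and the rate at which plasma free Neu5Ac returns to baseline levels". The other pharmacodynamic analyses in that section are optional. Section 7.2.3 adds that "Plasma concentrations of ManNAc and free Neu5Ac will be summarized descriptively by collection time points", with plots by dose. It also says that "Day 1 and Day 8 data for" Cmax and AUC over the dosing interval "may be compared to determine the accumulation ratio of the compound".

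The sampling is set out in Appendix D:

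- Day 1 is profiled to 12 h.
- Days 2-6 have one morning trough each, on weekdays only.
- "On Day 7, blood will be collected before the morning dose and at 0.5, 1, 2, 3, 4, 6, 8, 10 and 12 hours". On both profile days the 12 h draw is placed immediately before the evening dose.
- "On Day 90 (-5 days), blood will be collected for terminal PK at pre-dose" and out to 72 h, with drug withheld (4.5.3).

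Under 6.1, all subjects are planned to be on 6,000 mg BID after the first 7 days.

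**The concern.** Multiple-dose plasma PK and PD form a primary objective (2.1), and this model is the one pharmacodynamic analysis that 7.2.4 firmly promises. If the return to baseline is seen at one dose only, its dependence on dose cannot be estimated from observed returns. The analyst would then have to choose an indirect model after seeing data, or leave the analysis out. The accumulation ratio has a similar gap: the day it names has no PK sample.

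**Working it through.** No power or precision figure is given for this model, so the check sets the analysis against the schedule.

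**1. Where a return could be seen** (5.2.3, 4.5.1, 4.5.3, 6.1, Appendices C and D, Table 7)

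| Period | Planned dose | Neu5Ac samples | Return observed off drug? |
|---|---|---|---|
| Day 1 | 3,000 or 6,000 mg | 10, pre-dose to 12 h | No; next dose follows the 12 h draw |
| Days 2-6 | 3,000 or 6,000 mg BID | morning troughs | No |
| Day 7 | 3,000 or 6,000 mg BID (see step 3) | 10, pre-dose to 12 h | No; at most part of a within-interval decline |
| Days 45, 85, 180, 365, 548, 730 | 6,000 mg BID, all | troughs | No |
| Day 85-90 | 6,000 mg BID, all | 13, pre-dose to 72 h | Yes |
| Day 912 | 4,000 mg TID, all | 0, 2, 4, 6, 8, 24, 48 h | No; dosing continues, and the last three are troughs |

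The 5-7 days off drug before Day 912 end in a single pre-dose draw, again after 6,000 mg BID. Planned doses with a serially sampled return: 1. A dose relationship needs at least 2.

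**2. How far a 12 h window reaches.** Section 4.4.2 reports that, after a single dose, Neu5Ac is back at baseline by 24 h at 3,000 mg but still above it at 48 h at 6,000 mg. Table 1 gives median single-dose Tmax of 10 h and 11 h, so Day 1 has one scheduled sample (12 h) beyond the median peak at either dose. The share of single-dose AUC to infinity inside 12 h is at most Cmax × 12 / AUC:

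- 3,000 mg: 115 × 12 / 2147 = 0.64, so at least 36% lies later.
- 6,000 mg: 181 × 12 / 4171 = 0.52, so at least 48% lies later.

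This bound is approximate, because it combines a geometric-mean Cmax with a mean AUC. The conclusion rests on the schedule.

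**3. Day 8.** The blood PK row of Appendix D has 22 marks: baseline 1 + Day 1 10 + Days 2-6 1 + Day 7 10 = 22, which leaves Days 8-10 empty. Appendix C marks no PK blood on Days 8-10. Table 7 has no Day 8 row and shows 30 mL for PK on Day 7, which at 3 mL per sample is 10 samples. By Day 8 Cohort A is planned to have been escalated, so a Day 1 to Day 8 ratio there would mix dose change with accumulation.

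Two passages blur the Day 7 alternative. Section 5.2.3 lists only a trough on Day 7. Sections 4.1 and 4.8 place the escalation on Day 7 without a time of day, and Table 5 puts Day 7 in both phases.

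**4. What the planned samples can support.** For 6 v 6 on the log scale, the 95% interval for a ratio of geometric means is x/÷ exp(t × √(2/6) × √ln(1 + CV²)), with t = 2.228 on 10 degrees of freedom. The CV is an assumption; the documents give none for corrected Neu5Ac.

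- CV 30%: exp(2.228 × 0.577 × 0.294) = 1.46
- CV 50%: exp(2.228 × 0.577 × 0.472) = 1.84

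As a guide, the single-dose 6,000/3,000 ratio for Cmax in Table 1 is 1.6. An estimate of that size would carry an interval of 1.10 to 2.34 at the lower CV (1.6 / 1.46, 1.6 × 1.46) and 0.87 to 2.94 at the higher (1.6 / 1.84, 1.6 × 1.84).

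**The case against.** **Day 7 may carry information on loss.** A reader might infer that every Day 1-7 sample after the Neu5Ac peak is a 12 h trough. The documents do not support that for Day 7: the Table 1 medians are from fasted single doses. Under an illustrative linear model (formation half-life 4 h, loss half-life 12-48 h, both assumed), the Day 7 peak falls at 4.7-5.6 h, which puts the 6, 8, 10 and 12 h samples on a falling limb at both doses. This stands. A loss rate by dose could be inferred from such a decline and from the earlier rise, but that is not an observed return to baseline, and it needs a kinetic model. It is also not safe to put a precision or bias on this route: the same model, scaled to the Table 1 Cmax, implies 1.3-4.6 times the Table 1 AUC and 61-95% of peak at 24 h after 3,000 mg, against 4.4.2.

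**The population PK model already exists.** Section 3.8.4 describes a semi-mechanistic model fitted to the single-dose study and to this trial. This is a fair answer in substance, but 7.2.4 neither names it nor says that data are pooled.

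**Dose information will be reported anyway.** True: 7.2.3 commits to descriptive Neu5Ac summaries. It would be wrong to infer that the trial yields nothing on dose.

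**Other doses exist.** Appendix F lists 4,500 mg BID, but 6.1 and 7.3 plan no cohort at it, and Table 6 names it only as a possible lower dose after toxicity. Section 9.1.1 reports one dose reduction; subjects reduced for tolerability are not a designed contrast.

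**Little depends on it.** Section 7.1.1 treats testing as an aid to interpretation, no decision rule uses the model, the accumulation ratio is optional, and Day 8 may be a labelling slip. Section 5.2.3 also refers to Appendix D for time points. These points limit the severity.

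**Conclusion.** The concern holds. As written, the dose model in 7.2.4 rests on a return to baseline that is serially sampled off drug at one planned dose, 6,000 mg BID; a loss rate at 3,000 mg BID is reachable only indirectly, under a model the section does not specify. The optional accumulation ratio in 7.2.3 is tied to a day without PK samples.

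The severity is minor to moderate. The finding depends on the planned schedule and planned doses, not on any assumed half-life. It does not show that a dose effect on Neu5Ac is beyond estimation, nor that the accumulation ratio is lost, since Day 7 supplies a profile. The only assumption behind the figure for the replacement (x/÷ 1.5 to 1.8) that the documents cannot confirm is the between-subject CV of 30-50%.

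**What to change.** - **7.2.4:** replace the return-rate model with a comparison of Neu5Ac AUC over the 12 h interval, Cmax and Ctrough between the 3,000 and 6,000 mg BID groups on Days 1 and 7. Correct for each subject's Day 1 pre-dose value, or use that value as a covariate where a corrected value is not positive. Report ratios with 95% intervals, labelled exploratory because the cohorts are sequential, non-randomised and 6 v 6. Alternatively, name the population PK model of 3.8.4 as the source of dose dependence and say which data it pools.
- **Day 85-90:** report the return to baseline descriptively.
- **7.2.3:** change Day 8 to Day 7, and form the ratio within subject where the Day 1 and Day 7 doses are the same.
- **Reconcile** 5.2.3 with Appendix D on the Day 7 profile, and the passages on the timing of the Day 7 escalation, so that the dose behind Cohort A's Day 7 profile is explicit.
- **7.5:** record the change, and state that PK data from this study had already been modelled when it was made.

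The cost is wording and one recorded deviation. Appendix D and Table 7 already plan the samples, so no subjects, visits or blood are added.

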#### **7.2.5. Lectin Staining on Muscle Biopsies**

The fluorescence will be quantified in 5 different images per slide with  $\geq$  muscle cells per field and analyzed as a change from baseline to 90 days using a paired t-test.

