
## **2. OBJECTIVES AND SPECIFIC AIMS**

### **2.1. Primary Objectives**

The primary objectives of this study are:

- To assess the safety and tolerability of multiple doses of orally administered ManNAc to subjects with GNE myopathy;
- To examine plasma pharmacokinetics (PK) and pharmacodynamics (PD) of multiple doses of orally administered ManNAc to subjects with GNE myopathy;
- To determine the biochemical effect of ManNAc, as assessed by sialylation of proteins.

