### 3.7.2. Lectin Staining of Muscle Biopsies

Hyposialylation of muscle proteins is thought to play a major role in GNE myopathy, re-sialylation of muscle proteins would prove biological efficacy. Furthermore, hyposialylation has been correlated with decreased muscle performance in heterozygous GNE knockout mice. Lectin staining has been useful to demonstrate hyposialylation particularly of O-linked glycans in the muscle of the mouse model and subjects with GNE myopathy. Sialylation of muscle glycans recovered to normal levels in our GNE myopathy mouse model after ManNAc therapy. This method is the only reported reproducible, quantifiable assessment of muscle glycan hyposialylation in GNE myopathy to date. We feel that these convincing lectin-staining data justify acquiring muscle biopsies from GNE myopathy subjects in this study at baseline and after 3 months of therapy (see [Section 5.2.4.](#))

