#### **4.11. Randomization and Blinding**

There will be no blinding or randomization.

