### 5.2.4. Lectin and Antibody Labeling of Muscle Biopsies

Frozen slides acquired from subjects' muscle biopsies will be stained with fluorescent-labeled lectins and imaged by (quantitative) confocal microscopy. As mentioned, we and others have demonstrated by lectin staining that in particular O-linked glycans in GNE myopathy subjects and in a GNE myopathy mouse model are hyposialylated. Sialylation of muscle glycans recovered to normal levels in our GNE myopathy mouse model after ManNAc therapy. This method is the only reported reproducible, quantifiable assessment of muscle glycan hyposialylation in GNE myopathy to date (Figure 8).

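### The baseline versus 3-month muscle lectin comparison has no specified masking of visit, no full field-selection rule and no same-batch staining, although coding slides would be feasible and cheap in this open-label trial

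*Combined protocol and SAP*

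**What the plan says.** Section 2.1 lists among the primary objectives: "To determine the biochemical effect of ManNAc, as assessed by sialylation of proteins". Section 3.7.2 presents lectin staining as the way to see this in muscle. It says of the method, "This method is the only reported reproducible, quantifiable assessment of muscle glycan hyposialylation in GNE myopathy to date", and that re-"sialylation of muscle proteins would prove biological efficacy". The biopsies at baseline and 3 months are justified on that basis.

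The laboratory method is in Section 5.2.4: "Frozen slides acquired from subjects' muscle biopsies will be stained with fluorescent-labeled lectins and imaged by (quantitative) confocal microscopy". The analysis is in Section 7.2.5: "The fluorescence will be quantified in 5 different images per slide", with a minimum number of muscle cells per field (the number is missing from the text as read, which is not held against the plan). The result is then "analyzed as a change from baseline to 90 days using a paired t-test".

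On masking, Section 4.11 says only: "There will be no blinding or randomization". Sample coding appears in three places, each time for privacy: storage without personal identifiers (5.3.1), subject numbers or barcodes on research blood samples (10.1), and removal of identifiers from samples sent to outside laboratories (10.8). None of these conceals the visit.

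**The concern.** Open-label dosing explains why subjects and clinicians are unblinded. It does not explain why a person quantifying a frozen section should know whether it was taken before or during treatment. The hoped-for direction is known in advance: the Figure 8 legend reports low SNA and high VVA signal in patients, and a reversal of both in treated mice.

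The comparison is within subject, baseline against follow-up, with no untreated group. Anything that differs systematically between the two visits is therefore indistinguishable from treatment. That includes a reader's choice of fields and a staining or imaging session that differs by visit. At stake is the mechanistic conclusion that oral ManNAc restores sialylation in muscle, which rests on open biopsies taken twice from each subject.

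**Working it through.** **1. Is there a figure to reproduce?** No. The plan gives no effect size, variance, alpha, sidedness or power for the lectin endpoint. The 12 subjects in Section 7.3 are not derived from a formula. Everything below is an illustration under stated assumptions.

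**2. Effect of a visit-linked bias on the test.** Inputs: n = 12 pairs (Section 7.3) or n = 8 (assumed, if pairs are lost); paired t-test (Section 7.2.5); two-sided alpha 0.05 (assumed); no true change. Let d be the bias divided by the SD of the paired change. The test statistic is then noncentral t with n − 1 degrees of freedom and noncentrality d√n. For n = 12, d = 0.3 gives 0.3 × √12 = 1.04 and d = 0.5 gives 0.5 × √12 = 1.73. The probability of a significant result in either direction is:

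| Assumed bias d | n = 12 | n = 8 |
|---|---|---|
| 0 | 5.0% | 5.0% |
| 0.2 | 9.7% | 7.8% |
| 0.3 | 15.8% | 11.4% |
| 0.5 | 35.3% | 23.2% |
| 0.8 | 71.4% | 49.6% |

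For scale, 80% power at n = 12 needs a true change of 0.89 SD. A bias of 0.3 to 0.5 SD is thus 0.3/0.89 = 34% to 0.5/0.89 = 56% of that change.

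**3. Could field choice alone produce such a bias?** Take a field-to-field SD of s within a slide. Keeping the five highest of 6, 7 or 10 viewed fields shifts the slide mean by 0.25, 0.42 or 0.74 s. The extreme case is the lowest five at baseline and the highest five at follow-up. It was simulated with 12 pairs, 20,000 runs, no true change, and biopsy-level noise of SD 1 at each visit:

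| Field SD relative to biopsy SD | Best 5 of 6 | Best 5 of 7 | Best 5 of 10 | Fields chosen without regard to visit |
|---|---|---|---|---|
| 0.5 | 8.8% | 15.0% | 37.0% | 5.5% |
| 1.0 | 18.3% | 41.7% | 87.2% | 5.1% |

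These are worst cases, because selection is complete and runs in opposite directions at the two visits. The spread from 8.8% to 87.2% shows that the size depends wholly on quantities the documents do not give. The last column shows that the false-positive rate is about 5% when field choice is independent of visit. This covers selection bias only, not batch or biopsy-site differences.

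**The case against.** Five points can fairly be made against this.

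- **Silence is not evidence of poor practice.** A reader might infer that fields are picked by hand and that slides are in fact read unmasked. The documents say neither. They leave the selection method and the reading conditions unspecified, and a minimum-cell criterion does exist. This stands: the point is about what the plan secures.
- **The measurement is quantitative.** Section 5.2.4 has slides "imaged by (quantitative) confocal microscopy", and the Figure 8 legend reports constant microscope settings per lectin. This narrows the room for judgement mainly to field choice and settings. Bias would also have to push SNA and VVA in opposite directions, and WGA may serve as a partial internal check. That reduces the concern without closing it. The Figure 8 settings describe earlier images and are not carried into Section 7.2.5 as a commitment.
- **The tests are not confirmatory.** Section 7.1.1 treats all tests as aids to interpretation. This lowers the stakes, but the same section expects the results to inform later trials.
- **Lectin staining is not named in the objective.** Plasma sialylation is also listed. However, Section 7.2.4 makes its analysis optional, whereas Section 7.2.5 commits to a test of the lectin data.
- **It may be late.** Section 3.8.2.2 reports safety review through 24 months, so the 3-month biopsies have probably been collected. The documents do not say whether the slides have been stained or read. This affects which part of the fix is still available.

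**Conclusion.** The gap is real and worth closing. The plan excludes blinding in general and does not protect the muscle measure of a primary objective from visit-linked reading or batch effects. In a single-arm paired design these would count as drug effect. The false-positive figures of about 16% to 35% rest on an assumed bias of 0.3 to 0.5 SD, 12 complete pairs and a two-sided 5% test. They show sensitivity and do not estimate the bias in this trial.

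Two stronger readings are not supported. One is that the lectin result must be an artefact: the documents contain no evidence of biased reading. The other is that coding solves the problem at no cost. Coding removes reader expectation only. The follow-up biopsy is guided by a new MRI and taken from the contralateral muscle where feasible (Section 5.2.1.1.1), and there is no control group. Differences from either source would remain.

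**What to change.** Limit Section 4.11 to open-label dosing, and add to Section 7.2.5:

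- Slides are coded for subject and visit by existing staff who neither image nor quantify them.
- The five fields are taken by a pre-set random or systematic rule, moving to the next position when a field fails the minimum-cell criterion. The replacement step matters because a fixed position may land on fibro-fatty tissue.
- Both visits of a subject are stained and imaged in one batch at the same settings, where tissue allows.
- The code is broken only after quantification is locked.

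If slides have already been read, re-quantify retained slides or images under masking where they are available. Otherwise, state in the study report that reading was unmasked.

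The cost is protocol wording and relabelling, with no added subjects, biopsies or readers. There are two downsides. Someone outside the reading must hold the code. Batching also means that baseline tissue is stored longer than follow-up tissue, which is itself a difference between visits, so storage times should be recorded and reported.
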